H1: Older adults randomized to volunteering (vs. control) will report lower loneliness (H1a; UCLA Loneliness Scale)²⁷ and greater quality of life (H1b; WHOQOL Scale)²⁸ at 3, 6, 9, and 12 months.

Aim 2: *To examine increased social engagement, perceived usefulness, and perceived social support as mechanisms for reducing loneliness.*

H2: Older adults randomized to volunteering (vs. control) will report greater social engagement (H2a), perceived usefulness (H2b), and perceived social support (H2c) at 6 months, which will account for the effects on reduced loneliness at 12 months.

Aim 3: *To examine conditions under which volunteering is most effective at reducing loneliness.*

H3: The effect of volunteering vs. control on loneliness will increase with greater quantity (H3a; hours per month) and satisfaction (H3b).

H4 (exploratory): Given that functional impairment impacts all proposed mechanisms, the effect of volunteering vs. control on loneliness will be strongest for those with less functional impairment at baseline.

IMPACT: *National infrastructure for volunteering programs for older adults—The Senior Corps—ensures that volunteering is **highly scalable**. Dissemination and scaling up efforts will involve connecting primary care patients and aging services clients who are lonely with The Senior Corps, which we have shown to be feasible in our companion study, The Senior Connection. Existing infrastructure will make it possible to engage a large proportion of lonely older adults in volunteering, thereby reducing loneliness, improving well-being, and promoting health.*

II. CHARACTERISTICS OF THE RESEARCH POPULATION

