Credibility and Expectancy Questionnaire (CEQ)	Subject's expected benefits	Questionnaire to assess subject's expected benefits of the program	2 minutes Baseline and 12 month interview

Sexual Orientation Concealment Scale (SOCS)	Subject's concealment of sexual identity	Questions designed to assess lesbian, gay, and bisexual (LGB) individual's active concealment of their sexual minority status	2 minutes Baseline for those who answered as LGB on demographic form. 6 and 12 months – for those in volunteer group who had answered as LGB on demographic form at baseline.
Randomization Feedback	Subject's experience with randomization	Feedback from the subject on the randomization process and their satisfaction with the group to which they were randomized	5 minutes 12 month interview

Social connectedness measures

Measure Name and Citation	Construct Measured	Description & Psychometric Data	Estimated Administration Time
Revised UCLA Loneliness Scale, version 3 ²⁷	Global loneliness	Yields a continuous score, with greater scores indicating greater loneliness; it will be used to assess loneliness at all assessment time points. It has demonstrated excellent internal consistency, test re-test reliability, and construct validity (associations with social support and social network size), ²⁷ including with older adult samples. ^{13,27} Importantly, it has been shown to be sensitive to change as a result of intervention. ⁴⁰	3 - 5 mins all time points
De Jong Gierveld Loneliness Scale ⁴¹	Social and emotional loneliness	It had demonstrated excellent psychometric properties and construct validity.	3 - 5 mins all time points
Lubben Social Network Scale ⁴²	Social network size and frequency of contact.	This set of self-report questions has been shown to predict premature mortality.	3 – 5 mins; all time points
Interpersonal Needs Questionnaire (INQ) ^{43,44}	Thwarted belongingness (TB), perceived burdensomeness (PB).	[name] et al. ⁴³ report high internal consistency coefficients for the thwarted belongingness ($\alpha=.85$) and perceived burdensomeness subscales ($\alpha=.89$). In support of construct validity, both subscales were found to positively correlate with suicidal ideation.	3 – 5 minutes all time points

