Behavioral Activation Scale for Depression (BADS)—social subscale ⁴⁵	Social activation.	Kanter and colleagues present evidence of the scale's psychometric properties, including solid factor structure, internal consistency, and test-retest reliability.	2-4 minutes in-person interviews
Volunteer Functions Inventory ⁴⁶	Reasons individuals participate in volunteer activities	Konrath and colleagues demonstrated good psychometrics	3-5 minutes Volunteer condition only

		and a latent structure consistent with several subscales.	6 months and final interview
PROMIS Social Functioning Computerized Adaptive Tests ⁴⁷	Emotional support, informational support, instrumental support, satisfaction with social roles and activities, social isolation, companionship	These computerized adaptive tests measure several domains of social functioning.	5 – 7 minutes In-person interviews
Rosenberg Mattering to Others Scale ⁴⁸	Mattering to others (5 items)	This is the most commonly used measure of perceptions of mattering and has numerous reports of solid psychometrics	2 – 3 minutes In-person interviews

Quality of Life measures

Measure Name and Citation	Construct Measured	Description & Psychometric Data	Estimated Administration Time
WHOQOL-BREF ²⁸	Health-related quality of life	This brief 36 item measure assesses several domains of health related functioning and quality of life. It has excellent psychometric properties and can be used cross culturally.	10 - 15 minutes baseline and final interview
PROMIS Quality of Life scales ⁴⁹	General life satisfaction, Meaning and Purpose, Positive Affect	These measure several domains of quality of life. The purpose in life items have been empirically linked to volunteering in older adults. ⁵⁰	4 - 6 mins in-person interviews
Reminiscence Functions Scale ⁵¹	Measures reasons individuals engage in reminiscence, which is a key component of the life review intervention.	Robitaille et al. provide support for the 8 subscales and data that demonstrate adequate psychometric properties in a sample of older adults.	6 – 8 minutes Life review only 6 month and final interviews
Brief Measure of Generativity and Ego Integrity ⁵²	Generativity (perceptions of giving back, especially to younger generations) and ego integrity (looking back on one's life with meaning)	Vuksanovic and colleagues ⁵² provide data indicating that this shortened measure provides adequate construct coverage.	2 – 4 minutes In-person interviews

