
g) Analytic Procedures:

Power analysis is conducted to test treatment effects by the intent-to-treat (ITT) analysis for the primary hypothesis. We assume a conservative 20% attrition rate and a 0.3 within-subject correlation. A sample size of N = 300 (or N = 150 per treatment group) will allow us to detect a small effect size of 0.2 for loneliness, with 80% power based on a two-sided type I alpha = 0.05. The assumed within-subject correlation of 0.3 reflects the relatively long time lag between consecutive assessments. The proposed sample size also has 80% power to detect 32% mediation effects for loneliness, a continuous outcome. If full mediation is not achieved for any of the mediators considered, 32% mediation effects are sufficiently large to be of clinical importance for the outcomes of interest.

Descriptive statistics will be computed to summarize distributions of each outcome, with means and standard deviations for continuous outcomes and percent for categorical outcomes. Two-sample t tests (or the Mann-Whitney-Wilcoxon rank sum test) and Chi-squares will be used to examine balance of treatment randomization for continuous (if distributions are highlight skewed) and categorical variables. The primary hypotheses are concerned about the effectiveness of volunteering on reducing loneliness vs. control. Examination of mechanisms (mediation, Aim 2) as well as dose-response relationships (Aim 3) and moderators (Aim 3) of the intervention will also be examined. Aim 1 (and Aim 3 H4 on moderation) will be tested using longitudinal regression models, while the mediation hypothesis (Aim 2) will be examined by structural equation models, and dose-response relationships (Aim 3) by structural mean models.

The two most popular longitudinal models are the generalized linear mixed-effect models (GLMM) and the weighted generalized estimating equations (WGEE). Weighting is based on inverse probability of drop-out, extending standard GEE from valid inference only under missing completely at random to missing at random, similar to GLMMs. For inference about treatment effects, both models can be applied. However, parametric

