
Aim 1 compares subjects randomized to either the volunteering or control on loneliness (continuous variable). **H1a:** There will be a condition effect on loneliness at all time points indicating differing levels of loneliness in the direction: control > volunteering. Longitudinal models will be employed with loneliness as the response, and condition, time and their interaction as the predictors, controlling for age, gender. If a significant difference exists (a significant time by condition interaction), appropriate linear contrasts will confirm the hypothesized directional effects. For **H1b**, the same analytic strategy will be used, but with quality of life (continuous) as the response variable. Aim 2 involves mediation analysis: is to examine perceived usefulness and social support as mediators of the intervention effect on loneliness. **H2a:** Increases in social engagement at 6 months is hypothesized to mediate the effect of intervention condition on decreased loneliness at 12 months. The SEM-based mediation models will be applied, with social engagement as the mediator, intervention condition as the predictor and loneliness as the outcome, controlling for age, gender. If the null of full mediation is rejected, we will estimate direct, indirect and total effects to assess the strength of mediation. The same analytic strategy

will be used for perceived usefulness and social support (**H2bc**). **Aim 3** involves when volunteering will provide maximal benefit. **H3:** Greater hours (compliance) and satisfaction will be associated with better outcomes. We will apply the SFRM-based SMM to analyze dose-response relationships. We will first model dose using non-parametric methods and then characterize the patterns using parametric methods. This allows us to capture detailed dose and response relationships and provide more interpretable findings. **H4:** The longitudinal model for H1a will be used with functional status as a moderator variable.

h) Data and Safety Monitoring Plan:

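### The Aim 2 mediation models omit the baseline mediator and baseline loneliness and leave the mediator undefined as level or change; if it is the 6-month level, stable differences between people can pass for mediation.

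*Combined protocol and SAP*

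**What the plan says.** Section III.g (Analytic Procedures, Aim 2) words the hypothesis in terms of change: "Increases in social engagement at 6 months is hypothesized to mediate the effect of intervention condition on decreased loneliness at 12 months". The next sentence gives the model, "with social engagement as the mediator, intervention condition as the predictor and loneliness as the outcome, controlling for age, gender". The same strategy "will be used for perceived usefulness and social support", so one specification covers H2a to H2c.

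Section I (Specific Aims, H2) words it differently. Volunteers, compared with controls, "will report greater social engagement (H2a), perceived usefulness (H2b), and perceived social support (H2c) at 6 months". That is a comparison of levels between arms.

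No other part of the document adds a baseline term. The structural-equation text in III.g deals with estimators and fit indices. It cites a paper on longitudinal mediation but specifies no baseline covariate. Section II.d allows one further covariate, the amount of volunteering and informal caregiving, and only if the arms differ on it. The 2022 addendum does not touch the mediation model.

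The baseline data will exist. For the UCLA scale, section III.e says "it will be used to assess loneliness at all assessment time points". The social activation, PROMIS social functioning ("Emotional support, informational support, instrumental support, satisfaction with social roles and activities, social isolation, companionship") and mattering scales are scheduled at the in-person interviews. Baseline is one of these, and the addendum keeps it as a remote visit.

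**The concern.** Randomization makes the arms comparable, so it protects the path from condition to mediator. It does not protect the path from mediator to loneliness, because nobody is randomized to a level of engagement, usefulness or support. People who are habitually more engaged or better supported are likely to be less lonely at every visit. With only age and gender in the model, that standing association enters the mediator's slope. Multiplied by the effect of condition on the mediator, it becomes an indirect effect in the direction that H2 predicts. At stake is the Aim 2 conclusion that a mechanism accounts for the benefit, for any mediator that volunteering moves.

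**Working it through.** **The plan's own figure.** Section III.g claims 80% power to detect 32% mediation. This cannot be reproduced, because the two path sizes, the test and the definition of the percentage are not given. The check below asks what the stated model returns when the true mediator effect is zero.

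**Inputs from the plan.** Total effect on loneliness 0.2 SD ("detect a small effect size of 0.2 for loneliness, with 80% power based on a two-sided type I alpha = 0.05"); 300 randomized with 20% attrition, so 300 x 0.8 = 240 completers; within-subject correlation 0.3, used as the stable share r of loneliness.

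**Assumptions not in the documents.** The mediator has the same stable share r; the stable parts of mediator and loneliness correlate q = -0.3, -0.5 or -0.7; condition raises the mediator by a = 0.3 SD. All variables are scaled to SD 1 within arm.

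**Slope under the stated model.** Within arms, the covariance of the 6-month mediator with 12-month loneliness is c = r x q. The variance of the mediator is 1, so the false slope is c.

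**Slope with both baselines added.** Regress 12-month loneliness on the 6-month mediator, the baseline mediator and baseline loneliness. The two mediator readings are exchangeable in this set-up, so they share one coefficient b, and the normal equations give b = c(1 - r) / (1 + r - 2c²). For q = -0.7: c = -0.21 and b = -0.21 x 0.7 / (1.3 - 0.0882) = -0.147 / 1.2118 = -0.121.

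**False mediated share** = a x |slope| / 0.2. For q = -0.7: 0.3 x 0.21 / 0.2 = 31.5% as written, and 0.3 x 0.121 / 0.2 = 18% with baselines.

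**False-positive rate.** Simulation with 240 completers, counting trials in which both paths are significant at two-sided 0.05. Repeat runs differ by about 2 percentage points at most.

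| q | Slope as written | Share | False positives | Slope with baselines | Share | False positives |
|---|---|---|---|---|---|---|
| -0.3 | -0.090 | 13.5% | 19% | -0.049 | 7% | 8% |
| -0.5 | -0.150 | 22.5% | 41% | -0.084 | 13% | 17% |
| -0.7 | -0.210 | 31.5% | 59% | -0.121 | 18% | 32% |

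**Sensitivity to the assumptions.**
- Effect on the mediator: at q = -0.5, a = 0.2 gives 0.2 x 0.15 / 0.2 = 15%, and a = 0.5 gives 37.5%.
- No effect on the mediator (a = 0): the mean indirect effect is about zero, and the false-positive rate stays at or below 5% for all three values of q.
- Stable share 0.5 with a = 0.3: the share runs from 22.5% to 52.5% over q = -0.3 to -0.7, and from about 8% to 21% with both baselines.
- Change score as mediator: its covariance with 12-month loneliness is rq - rq = 0. The false slope vanishes, and joint significance occurs in about 2% to 3% of runs.

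**The case against.** The strongest reply is that the plan never says levels are analysed. It speaks of increases, and a change score would remove this particular bias in the set-up above. A reader might infer from the model sentence that the trial will certainly analyse levels. The documents do not establish that: the model sentence names the construct without defining the variable, section I points to levels, and the Aim 2 text points to change. What stands is that the variable is undefined, that the level is the plainer reading of the model sentence, and that the answer decides whether the bias is present.

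Second, a reader might infer that all three mediators will show false mediation. That needs volunteering to move each of them. H2 predicts this, but it is not known.

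Third, the 31.5% lies close to the plan's 32% benchmark only because of the inputs q = -0.7 and a = 0.3, which the documents do not supply. Milder inputs give less than half as much.

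Fourth, joint significance is not the plan's decision rule. The plan separates direct, indirect and total effects once a null hypothesis of full mediation has been rejected. Taking a test of the direct effect as a proxy for that rule, at q = -0.7 rejection occurs in roughly 18% to 20% of runs as written and 26% to 28% with baselines. Under that rule the added covariates change the decision only modestly. Their main gain is in the size of the estimated indirect effect.

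Finally, Aim 2 concerns mechanism. The primary comparison of loneliness between arms does not depend on it.

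**Conclusion.** The point holds in a conditional form. As written, the models for H2a to H2c adjust for age and gender alone and do not say whether the mediator is a level or a change. If the 6-month level is used and volunteering moves the mediator, stable between-person correlation inflates mediation in the hypothesized direction. Over the range shown at stable share 0.3 and a 0.3 SD effect on the mediator, an absent mechanism would appear to explain 13.5% to 31.5% of the total effect. These sizes illustrate and do not predict: the effect on the mediator, the correlation of the stable parts and the mediator's stable share are all assumed.

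A reader might also infer that adding the baselines cures the problem. It does not. One baseline reading is a noisy measure of the stable part, and 55% to 58% of the false slope remains in these three cases (0.049/0.090 to 0.121/0.210).

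**What to change.** In section III.g, Aim 2, extend the covariates for H2a to H2c to age, gender, the baseline value of the mediator and baseline loneliness, in both the mediator equation and the outcome equation. State that the mediator is the 6-month score, name the scale that measures each mediator, and reconcile the wording of H2 in section I with that of section III.g.

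State also that the mediator-to-loneliness path is observational and that baseline adjustment reduces confounding without removing it. Add a sensitivity analysis showing how strong residual confounding of that path would have to be to account for the estimated indirect effect.

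The cost is a few sentences and a little more analysis. No new data are needed, since loneliness and the candidate mediator scales are already scheduled at baseline. The estimated mediated share will probably be smaller. Fixing the covariates in advance also prevents their being chosen after the results are seen.

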GLMM requires distribution assumptions, making inference sensitive to departures from assumed distributional models.⁵⁹⁻⁶¹ The semi-parametric WGEE requires no such assumption, thereby providing valid inference for a broader class of data distributions. We will use both models; if discrepancy arises between the two, we will report the results based on WGEE. Both models address missing data under the missing at random (MAR) mechanism.⁶²⁻⁶⁴ Biased estimates may still arise if missingness follows the non-ignorable non-response (NINR) mechanism. Although quite rare, and we do not anticipate such a missing data mechanism in this study, we will examine this issue by performing sensitivity analyses under some non-ignorable missing data models.^{59,65} Structural equation models (SEM) will be applied to test the mediation hypothesis involving the putative mediators of usefulness and social support.⁶⁶ Again, the popular maximum likelihood (ML), generalized least squares (GLS), and weighted least square (WLS) estimates are all biased under MAR, if parametric assumptions are not met by data in the study.^{67,68} We will also use recent distribution-free methods for more robust inference.⁶⁷ If results differ significantly between the maximum and distribution-free methods, only estimates from the latter will be reported. Common indices for assessing goodness-of-fit include likelihood ratio, Akaike (AIC) and Bayesian criteria. For SEM, popular goodness-of-fit measures include chi-square test, the comparative fit index (CFI), the index of Tucker and Lewis (TLI), and Root Mean Square Error of Approximation (RMSEA).^{66,69,70}

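### Aim 2 ties its mediation estimates to rejecting full mediation, gives no branch for non-rejection, and names no test of the indirect effect

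*Combined protocol and SAP*

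**What the plan says.** The first clause of H2 (section I, Specific Aims) is that volunteers "will report greater social engagement (H2a), perceived usefulness (H2b), and perceived social support (H2c) at 6 months". Its second clause makes these three mediators the explanation of the treatment effect: "which will account for the effects on reduced loneliness at 12 months".

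Section III.g, Analytic Procedures, fits a structural equation model for Aim 2 with condition as predictor, one mediator, and loneliness as outcome, adjusted for age and gender. The decision rule is: "If the null of full mediation is rejected, we will estimate direct, indirect and total effects to assess the strength of mediation". The same strategy is then carried over to perceived usefulness and social support.

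The paragraph on structural equation models in that section names estimators (likelihood-based, least-squares and distribution-free) and measures of model fit. It gives no test or confidence interval for the indirect effect. The power paragraph adds: "If full mediation is not achieved for any of the mediators considered, 32% mediation effects are sufficiently large to be of clinical importance". No section says what is estimated, reported or concluded when the null of full mediation is not rejected.

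**The concern.** The quantity that H2 concerns is the indirect effect: the part of the 12-month difference that runs through the mediator. The only null hypothesis stated for Aim 2 concerns the other part, the direct effect. Estimates of all three effects are promised in the case where the direct effect is shown to be non-zero.

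That condition works against the hypothesis. The better a mediator explains the treatment effect, the smaller the direct effect, and the less often the written condition is met. Non-rejection is also the expected result when volunteering does nothing at all, so by itself it is not informative about mechanism. With no stated branch and no named inference for the indirect effect, the central result of Aim 2 is left to choices made after the data are seen, for three mediators.

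**Working it through.** The plan gives no figure for how often its condition would be met, so there is none to reproduce. The check is how that frequency moves with the share mediated.

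**Inputs from section III.g:** 300 randomised, 150 per arm; 20% attrition, giving 0.8 × 300 = 240 analysed; effect size 0.2; two-sided alpha 0.05. That alpha is stated for the primary hypothesis; the full-mediation test has none, so 0.05 is assumed. The 32% share is used because the plan calls it clinically important.

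**Assumed:** within-arm SD of 1 for mediator and loneliness, and the mediator shift *a* (arm difference in SD), which the documents do not give and which is therefore varied.

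**Set-up.** Let *c* be the total effect, *p* the share mediated and *b* the mediator-to-loneliness slope. Then *b* = *pc*/*a* and the direct effect is *c′* = (1 − *p*)*c*.

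**Chance that the condition is met.** SE(*c′*) = √[(1 − *b*²)(4 + *a*²)/N], *z* = *c′*/SE, and the probability is Φ(*z* − 1.96) + Φ(−*z* − 1.96).

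Worked cases at *c* = 0.2, N = 240:
- None mediated, *a* = 0: SE = √(4/240) = 0.1291, *z* = 1.549, probability 34%. With *a* = 0.8: SE = √(4.64/240) = 0.1390, *z* = 1.438, probability 30%.
- 32% mediated, *a* = 0.36: *b* = 0.064/0.36 = 0.178, *c′* = 0.136, SE = √(0.9684 × 4.1296/240) = 0.1291, *z* = 1.054, probability 18%.
- All mediated: *c′* = 0, so the probability is alpha, 5%, for any *a*.

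| Total effect | Share mediated | Mediator shift (SD) | N = 240 | N = 300 |
|---|---|---|---|---|
| 0.2 SD | none | 0–0.8 | 30–34% | 36–41% |
| 0.2 SD | 32% | 0.2–0.8 | 17–20% | 20–24% |
| 0.2 SD | all | any | 5% | 5% |
| 0 | none | 0 | 5% | 5% |

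Simulation of the 32% and all-mediated cases at *a* = 0.36 (20,000 trials each) agrees: 17.8% / 21.4% and 4.8% / 5.1%.

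**Larger total effects, N = 240.** With 32% mediated and shifts of 0.36–0.8 SD, the condition is met in about 43–50% of trials at 0.36 SD and 70–83% at 0.5 SD. With none mediated at 0.5 SD it is met in about 95–97%. With all mediated it is 5% again.

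**Power of an indirect-effect test.** Requiring both paths to be significant, power ≈ Φ(*a*/√(4/N) − 1.96) × Φ(*b*/√((1 − *b*²)/N) − 1.96). For 32% of 0.2 SD, *a* = 0.36, N = 240: Φ(2.789 − 1.96) × Φ(2.799 − 1.96) = 64%.
- 32% of 0.2 SD mediated, shifts of 0.2–0.8 SD: 24–64% (N = 240) or 28–77% (N = 300). A shift of 0.36 SD is close to the best case; the lowest values are at 0.8 SD.
- All of 0.2 SD mediated: 49% / 58% at a shift of 0.25 SD and 98% / 99% at 0.8 SD, peaking above 99% in between.

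**The case against.** Several objections have force.

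- **The text says *if*, not *only if*.** This stands. The plan does not undertake to withhold the indirect effect. It also says that structural equation models will test the mediation hypothesis, and it states: "The proposed sample size also has 80% power to detect 32% mediation effects for loneliness, a continuous outcome". Both suggest that a wider assessment was intended, and the cited distribution-free methods may carry their own inference. What remains is that no other branch is written and no test is named.
- **H2 names three mediators, not one.** This also stands. The 5% floor applies when the single mediator being tested carries everything. If three independent mediators each carry a third (shift 0.5 SD, N = 240), each single-mediator model meets the condition in about 16%, 45% and 76% of trials at total effects of 0.2, 0.36 and 0.5 SD.
- **0.2 SD is the effect the trial is sized to detect, not the one expected.** A reader might infer that the estimates usually go missing whenever H2 is true, or that a non-significant direct effect is the likelier result whenever H2 is false. Neither holds in general, as the results for larger effects show.
- **Other steps limit misreading.** Showing first that condition affects the mediator, or loneliness at 12 months, would help. For H1a the plan says: "If a significant difference exists (a significant time by condition interaction), appropriate linear contrasts will confirm the hypothesized directional effects". It makes neither step a condition for Aim 2.

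Three stronger readings are not supported. A reader might infer that non-rejection will be declared full mediation; the power paragraph's phrase about full mediation not being achieved invites that, but no sentence says it. A reader might infer that the stated 80% mediation power is wrong; its test and path values are not given, so it can be neither confirmed nor refuted. A reader might infer that baseline values are wrongly left out of the model; the wording about increases and decreases leaves open whether change from baseline is analysed. The last two form no part of this point.

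**Conclusion.** The concern holds as a gap in the Aim 2 decision rule. The direction follows from the rule itself: for a fixed total effect, the chance of meeting the condition falls to alpha as the tested mediator comes to carry the whole effect. That floor is the same as under no effect, so non-rejection cannot distinguish the two.

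The size depends on the total effect. At 0.2 SD the estimates are promised in a minority of trials whatever the share mediated; at 0.5 SD with 32% mediated they are promised in most. The figures rest on unit SDs, alpha 0.05 for the full-mediation test and assumed mediator shifts. How often an indirect-effect test would succeed depends strongly on that shift, so no single power figure should be quoted for it.

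This is a mechanism aim and the primary treatment comparison is unaffected. The change should be made, but it does not threaten the trial's main conclusion.

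**What to change.** In section III.g, replace the conditional sentence for Aim 2. For each of the three mediators:

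- estimate direct, indirect and total effects with confidence intervals, whatever the direct-effect test shows;
- test the indirect effect with a named method, such as a bootstrap or product-distribution interval, at a stated alpha;
- state that a non-significant direct effect is not evidence of full mediation.

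The cost is a few sentences of analysis wording. No new data, visits or participants are needed.
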